13 PUBLICATION PLAN

All publication rights are delineated in the Clinical Study Agreement and/or other separate agreements with the Investigator and/or Institution, as applicable.

14 CONFLICT OF INTEREST POLICY

14.1 Finance, Insurance, and Indemnity

Arrangements for finance, insurance, and indemnity are delineated in the Clinical Study Agreement and/or other separate agreements with the Investigator and/or Institution, as applicable.

16 APPENDICES

Appendix A Prohibited and Restricted Medications

The table below lists prohibitions and restrictions by medication class, including representative medications within class. A **prohibited** medication is not allowed. A **restricted** medication is allowed only under certain conditions. Details regarding procedures for subjects who take a prohibited or restricted medication during the study are provided in [Section 4.6.1](#).

Medication Class	Medication ^a	Prohibition/restrictions
Antipsychotics other than pimavanserin and quetiapine as study drug	PROHIBITED All in class	
Must be washed out 2 weeks or 5 half-lives (whichever is longer) prior to BaselineProhibited throughout the study until completion of the EOT visit
Anticholinergics	PROHIBITED 
Centrally acting anticholinergics
benztropinebiperidentrihexiphenidyloral diphenhydramine	Anticholinergic medications whose primary mechanism of action is centrally acting are prohibited and must be washed out and discontinued at least 2 weeks or 5 half-lives (whichever is longer) prior to Baseline
	UNRESTRICTED 
peripherally acting anticholinergicstopical diphenhydramine	Oxybutynin and other anticholinergics may be used if dose unchanged for at least 4 weeks prior to Baseline and dose is expected to remain unchanged throughout the study until completion of the EOT visit.
Anticonvulsant and mood stabilizers	PROHIBITED 
carbamazepinelamotriginelithiumphenytoin	
Must be washed out 5 half-lives prior to BaselineProhibited throughout the study until completion of the EOT visit
	RESTRICTED 
valproate	Valproate may be used if dose unchanged for at least 4 weeks prior to Baseline and dose is expected to remain unchanged until completion of the EOT visit.
Antidepressants	PROHIBITED 
mirtazapinenefazadonefluvoxaminemianserintrazodoneamitriptyline	
Prohibited throughout the study until completion of the EOT visitMust be discontinued at least 2 weeks or 5 half-lives (whichever is longer) prior to the Baseline visit

Medication Class	Medication ^a	Prohibition/restrictions
	
 • nortriptyline • imipramine • trimipramine • desipramine • clomipramine • esketamine • ketamine 	
	RESTRICTED 
 • citalopram • escitalopram • venlafaxine 	
 • If subject is remaining on these medications, the dose of the permitted antidepressants on the left must be unchanged for at least 4 weeks prior to Baseline and is expected to remain unchanged until completion of the EOT visit. If the medication is being discontinued, it must be discontinued at least 2 weeks or 5 half-lives (whichever is longer) prior to the Baseline visit. 
 ◦ Citalopram is restricted to a maximum dose of 20 mg/day. ◦ Escitalopram is restricted to a maximum dose of 10 mg/day. ◦ Venlafaxine is restricted to a maximum dose of 225 mg/day
Anxiolytics	PROHIBITED 
 • chlordiazepoxide • diazepam • flurazepam 	Prohibited at Baseline and throughout the study until completion of the EOT visit
	RESTRICTED 
 • alprazolam • clonazepam • lorazepam • oxazepam • temazepam • midazolam • triazolam 	
 • Short- or medium-acting benzodiazepine may be used for acute anxiety. Reasonable efforts should be made to use minimum dose necessary for symptom management. • May not be used within 12 hours prior to an assessment visit
Hypnotics and sleeping agents	PROHIBITED 
 • zolpidem • zopiclone • eszopiclone 	Prohibited at Baseline and throughout the study until completion of the EOT visit
	RESTRICTED 
 • zaleplon • ramelteon 	May not be used within approximately 12 hours prior to an assessment (including assessments on handheld device and in clinic), and efforts should be made to limit agents to lowest dose for the shortest time needed.

Medication Class	Medication ^a	Prohibition/restrictions
Stimulants and wake-promoting agents	PROHIBITED 
 • methylphenidate • modafinil • armodafinil 	Prohibited at Baseline and throughout the study until completion of the EOT visit (see Section 6.3.7 for procedures related to a positive amphetamine test at study entry)
Non-stimulant ADHD medications	PROHIBITED 
 • atomoxetine 	Prohibited at Baseline and throughout the study until completion of the EOT visit
Serotonin antagonists	PROHIBITED 
 • ciproheptadine 	
 • Prohibited throughout the study until completion of the EOT visit • Must be discontinued at least 3 weeks prior to the Baseline visit
Antiarrhythmic drugs	PROHIBITED 
 • ajmaline • amakalant, semantilide • amiodarone • bretylium • disopyramide • dofetilide • dronedarone • flecainide • ibutilide • procainamide • propafenone • quinidine • sotalol, d-sotalol 	Prohibited at Baseline and throughout the study until completion of the EOT visit
Opioids	PROHIBITED 
 • methadone 	Prohibited at Baseline and throughout the study until completion of the EOT visit
Antimicrobials, antifungals, and antimalarials	PROHIBITED 
 • clarithromycin • erythromycin • levofloxacin • moxifloxacin • pentamidine • roxithromycin 	Prohibited at Baseline and throughout the study until completion of the EOT visit
	RESTRICTED 
 • artenimol/piperaquine • azithromycin 	
 • Prohibited at Baseline but may be used during the course of the study to treat a bacterial infection (e.g., urinary tract infection, respiratory infection), post-Baseline at the discretion of the Principal Investigator.

Medication Class	Medication ^a	Prohibition/restrictions
	
• bedaquiline• ciprofloxacin• gemifloxacin• norfloxacin• ofloxacin• fluconazole• telavancin• telithromycin	
• The medications on the left are only allowed under the following conditions:
○ The subject has a Baseline ECG with a QTcF <425 ms IF QRS duration is <120 ms OR○ The subject has a QTcF <450 ms at Baseline IF QRS duration \geq120 ms

^a Medications within each class include but are not limited to the examples listed in this table.

Appendix B Prohibited and Restricted Concomitant Medications: Inhibitors and Inducers of Cytochrome P450 Enzyme 3A4

The information presented here is intended to provide guidance and does not constitute an exhaustive list of strong CYP 3A4 enzyme (CYP3A4) inhibitors and inducers. Any questions should be discussed with the Medical Monitor or appropriate designee. Details regarding procedures for subjects who take a prohibited or restricted medication during the study are provided in [Section 4.6.1](#).

The metabolism of pimavanserin is affected by strong CYP3A4 inhibitors, resulting in an increase in maximum plasma concentration (C_{max}) and area under the plasma concentration-time curve (AUC) of approximately 3-fold.

Strong inhibitors of CYP3A4 are to be stopped at least 7 days or 5 half-lives prior to investigational product administration, whichever is longer. Strong inducers of CYP3A4 are to be stopped 30 days or 5 half-lives prior to investigational product administration, whichever is longer. Moderate inhibitors and inducers of CYP3A4 are allowed but should be used with caution.

STRONG INHIBITORS	MODERATE INHIBITORS	INDUCERS
grapefruit juice ^a boceprevir (Victrelis [®]) clarithromycin (Biaxin [®]) cobicistat (part of Stribild [®]) conivaptan (Vaprisol [®]) fluvoxamine (Luvox [®]) indinavir (Crixivan [®]) itraconazole (Sporanox [®]) ketoconazole (Nizoral [®]) lopinavir and ritonavir (Kaletra [®]) mibepridil (Posicor [®]) nefazodone (Serzone [®]) nelfinavir (Viracept [®]) posaconazole (Noxafil [®]) quinupristin (Synercid [®]) ritonavir (Norvir [®] , part of Viekira Pak [™]) saquinavir (Invirase [®]) telaprevir (Incivek [®]) telithromycin (Ketek [®]) voriconazole (Vfend [®])	grapefruit juice ^a amprenavir (Agenerase [®]) aprepitant (Emend [®]) atazanavir (Reyataz [®]) ciprofloxacin (Cipro [®]) darunavir/ritonavir (Prezista [®] /Ritonavir) diltiazem erythromycin (Erythrocin [®] Lactobionate) fluconazole (Diflucan [®]) fosamprenavir (Lexiva [®]) imatinib (Gleevec [®]) verapamil (Calan [®])	

STRONG INDUCERS	avasimibe carbamazepine (Tegretol®) phenobarbital (Luminal®, Solfoton®) phenytoin (Dilantin®) rifampin (Rifadin®, Rifadin® IV, Rimactane®) St. John's Wort	MODERATE INDUCERS	bosentan (Tracleer®) efavirenz (Sustiva®) etravirine (Intelence®) modafinil (Provigil®) nafcillin (Unipen®, Nallpen®)
-----------------	---	-------------------	---

^a The effect of grapefruit juice varies widely among brands and is concentration-, dose-, and preparation-dependent. Studies have shown that it can be classified as a “strong CYP3A inhibitor” when a certain preparation was used (e.g., high dose, double strength) or as a “moderate CYP3A inhibitor” when another preparation was used (e.g., low dose, single strength). (FDA Drug Development and Drug Interactions <http://www.fda.gov/Drugs/DevelopmentApprovalProcess/DevelopmentResources/DrugInteractionsLabeling/ucm093664.htm#classInhibit>).

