4.6.1 Permitted, Restricted, and Prohibited Medications

Prohibitions and restrictions for concomitant medications should be followed between the initial screening visit and Week 4/Visit 6/ET as specified in [Appendix A](#) and [Appendix B](#). These appendices do not constitute an exhaustive list and any questions regarding prohibited and restricted medications should be discussed with the Medical Monitor or designee.

Use of medications that could interfere with study conduct or any questions regarding prohibited and restricted concomitant medications should be reviewed and/or discussed with the Medical Monitor or designee.

Medications that can prolong QT interval are prohibited (or restricted if approved by the Medical Monitor) as specified in [Appendix A](#).

Permitted concomitant medications should remain at a stable dose throughout the study.

If a subject is on a medication restricted by the protocol, the medication should be adjusted if it is determined by the Investigator to be clinically appropriate (e.g., if the subjects symptoms are not well-controlled or if the subject cannot tolerate the current medication) in consultation with the treating physician.

Subjects who require current treatment with a prohibited medication will be withdrawn from the study.

Subjects who have previously taken a prohibited medication during the study will be withdrawn from the study unless:

- the prohibited medication has been discontinued AND
- withdrawal from the study presents an unacceptable medical risk to the subject

The justification to allow the subject to continue in the trial will be made by the Sponsor/Medical Monitor, with medical input from the Investigator, and will be documented. If a subject is allowed to remain in the trial, this will be reported as a major protocol deviation and not a waiver.

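### Appendix A lets telithromycin be started after Baseline, but Appendix B lists it as a strong CYP3A4 inhibitor to be stopped before study drug, and Section 4.6.1 does not say which rule governs

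*Protocol*

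**What the plan says.** Three parts of the protocol bear on this.

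**Appendix A, antimicrobials, restricted row.** Ten agents are listed, telithromycin among them. The rule is "Prohibited at Baseline but may be used during the course of the study to treat a bacterial infection", at the discretion of the Principal Investigator. It continues "The medications on the left are only allowed under the following conditions", followed by two limits: Baseline QTcF below 425 ms if QRS is under 120 ms, or below 450 ms if QRS is 120 ms or more. The row has no CYP3A4 condition and does not refer to Appendix B.

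**Appendix B.** Telithromycin is named under strong CYP3A4 inhibitors. The reason for the list is given as "The metabolism of pimavanserin is affected by strong CYP3A4 inhibitors", with Cmax and AUC rising about 3-fold. The rule is "Strong inhibitors of CYP3A4 are to be stopped at least 7 days or 5 half-lives prior to investigational product administration, whichever is longer". For the weaker class the text says "Moderate inhibitors and inducers of CYP3A4 are allowed but should be used with caution". The appendix opens by saying "The information presented here is intended to provide guidance" and that the list is not exhaustive.

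**Section 4.6.1.** One rule, which points to both appendices, reads "Prohibitions and restrictions for concomitant medications should be followed between the initial screening visit and Week 4/Visit 6/ET as specified in". Another, which points to Appendix A alone, reads "Medications that can prolong QT interval are prohibited (or restricted if approved by the Medical Monitor) as specified in". The section sends questions to the Medical Monitor. It has no rule for a drug that the two appendices treat differently.

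**The concern.** A site that follows the Appendix A row exactly could start a strong CYP3A4 inhibitor in a subject who is taking study drug every day. The row's ECG condition uses a Baseline value, which precedes study drug and so cannot reflect any later rise in exposure. Pimavanserin has its own QT warning; Section 1.3.1 gives an average prolongation of about 5 to 8 ms at 34 mg. Section 3.1.2 does not allow the dose of study drug to be decreased. Under Section 5.1.5 the investigator is blinded and does not know whether the subject is on pimavanserin.

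The label also decides how the case is handled. Section 4.6.1 withdraws a subject who requires a prohibited medication, whereas a restricted medication is allowed under its conditions. Two sites could treat the same prescription differently, each with support in the text.

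**Working it through.** No sample size, power or error rate is involved. The check compares the two lists and then reads the rules together.

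**Step 1: drugs named in both appendices.**

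| Drug | Appendix A | Appendix B class | Comparison |
|---|---|---|---|
| clarithromycin, fluvoxamine, nefazodone | prohibited | strong inhibitor | agree |
| carbamazepine, phenytoin | prohibited | strong inducer | agree |
| telithromycin | restricted; post-Baseline start permitted | strong inhibitor | A permits, B's class rule excludes |
| ciprofloxacin, fluconazole | restricted; post-Baseline start permitted | moderate inhibitor | compatible after Baseline; A stricter at Baseline |
| erythromycin | prohibited | moderate inhibitor | A stricter |
| modafinil | prohibited | moderate inducer | A stricter |

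The count is 3 + 2 + 1 + 2 + 1 + 1 = 10 drugs. Strong inhibitors number 3 + 1 = 4. Appendix A prohibits three of these four and permits one, telithromycin, after Baseline.

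**Step 2: direction of each difference.** For erythromycin and modafinil the documents also differ, but a site that follows Appendix A is already on the safer side. The same holds for ciprofloxacin and fluconazole at Baseline. Only for telithromycin does following Appendix A lead to something that Appendix B's class rule is meant to prevent.

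**Step 3: do the rules resolve themselves?**
- *Cumulative reading.* Section 4.6.1 tells sites to follow both appendices. Appendix A's limits are necessary conditions and need not exempt a drug from Appendix B. Appendix B expressly allows only moderate inhibitors and inducers. On this reading telithromycin is barred.
- *Literal reading.* Appendix B calls itself guidance and states a stop before dosing. It does not mention a strong inhibitor started later. Appendix A expressly permits a later start. On this reading telithromycin is allowed.

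The protocol does not choose between the two readings.

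**Step 4: reach.** Telithromycin is 1 of the 10 restricted antimicrobials, so moving it leaves 10 − 1 = 9. The stated exposure effect concerns pimavanserin, one of three arms randomized 1:1:1. SAP Section 19 gives 11 subjects randomized in total, and neither document reports any telithromycin use.

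**The case against.** The strongest reply is that the appendices were always meant to be read together, with the stricter rule governing. Section 4.6.1 points that way, and the other overlaps cause no difficulty once it is assumed. It is the more sensible reading. It is not written down, though, and a site looking up an antibiotic finds an explicit permission in the Appendix A row with nothing pointing to Appendix B.

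A second reply is that if Appendix B is only a pre-dose rule, there is no contradiction, just silence about strong inhibitors started after Baseline. That is partly right. The silence would cover strong inhibitors named only in Appendix B, and moving one drug would not fill it. For telithromycin, however, the protocol is not silent: it grants permission.

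A third reply is that safeguards exist, and they carry real weight:
- Telithromycin is not admitted on QTcF limits alone, as a quick reading of the row might suggest. A bacterial infection and the Principal Investigator's judgement are also required, and Section 4.6.1 mentions Medical Monitor approval for restricted QT-prolonging drugs.
- Subjects may not take medication without consulting the Investigator, except in an emergency (Section 4.6).
- ECGs are scheduled at Baseline and at Weeks 1 to 4 (Table S-1) and are centrally read (Section 6.3.4).
- Study drug can be interrupted (Section 7.2.2.3), the subject withdrawn (Sections 3.1.2 and 4.4), or the blind broken in an emergency (Section 9.7).

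These limit harm, but most act after exposure has begun, and none corrects the instruction.

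**Conclusion.** The inconsistency stands, and it is minor. One drug is permitted during dosing by one appendix and excluded by the class rule of the other, with no stated precedence. The conclusion rests on the two lists as printed and on reading Appendix B's class rule, together with its allowance for moderate agents only, as intended to keep strong inhibitors away from study drug.

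Four stronger readings are not supported:
- *That telithromycin is the only drug treated differently by the two appendices.* Erythromycin and modafinil differ too, in the safe direction.
- *That co-administration would take subjects beyond the doses tested for QT effect.* If exposure were dose-proportional, 3 × 34 mg = 102 mg would exceed the 17 to 68 mg range in Section 1.3.1. The documents do not state proportionality, and the 3-fold figure describes the class, not telithromycin.
- *That any subject was affected.* The documents report no such use.
- *That the analysis is affected.* No statistic changes.

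The study was permanently stopped as of 24 September 2020 (SAP Section 3.6) after 11 subjects were randomized. The correction therefore matters mainly for classifying any use that did occur and for any later protocol that reuses the text.

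**What to change.** Move telithromycin from the restricted to the prohibited antimicrobials in Appendix A, prohibited through completion of the EOT visit. Optionally add one sentence to Section 4.6.1 stating that when a drug appears in both appendices, the stricter status applies. That sentence would also confirm Appendix A's status for erythromycin and modafinil. It would not reach strong inhibitors named only in Appendix B.

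The cost is protocol wording only; the SAP, sample size and analyses are untouched. The clinical price is one fewer antibiotic option, with nine restricted antimicrobials remaining, and withdrawal under Section 4.6.1 of any subject who requires telithromycin.

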1.2.2 Quetiapine

Quetiapine is a second-generation antipsychotic that has affinity for D₂, 5-HT_{2A}, H₁, alpha 1 and 5-HT_{1A} receptors. Its precise mechanism of action is unknown, but according to the dopamine theory of schizophrenia, antipsychotic effects might be related to the drug's ability to reduce dopaminergic neurotransmission in the mesolimbic pathway.

Quetiapine immediate-release is an orally administered antipsychotic approved in the United States for the treatment of schizophrenia, acute treatment of manic episodes associated with bipolar I disorder, depressive episodes associated with bipolar disorder, and maintenance treatment of bipolar I disorder ([Northstar Rx LLC. 2019](#)). The extended-release formulation is approved in the US for use as adjunctive treatment to antidepressant therapy of major depressive disorder. Quetiapine is also commonly used in off-label indications such as behavioral and psychological symptoms of dementia, posttraumatic stress disorder, depression psychosis in Parkinson's disease, anxiety disorders and insomnia ([El-Saifi et al. 2016](#)). In randomized controlled trials that recruited relatively younger and healthier populations, as opposed to the patients prescribed the medication in clinical

practice, the most frequent quetiapine side effects included somnolence (18%), dizziness (11%), dry mouth (9%), constipation (8%), orthostatic hypotension (4%), weight gain (5%), and lethargy dyspepsia (5%) ([El-Saifi et al. 2016](#)).

In April 2005, the US Food and Drug Administration (FDA) issued a warning about the increased risk of mortality associated with the use of second-generation antipsychotics in older adults with dementia-related psychosis, based on the analyses of 17 placebo-controlled trials. Most of the deaths were cardiovascular (e.g., heart failure, sudden death) or infectious (e.g., pneumonia) in nature. The quetiapine prescribing information also includes a warning regarding QT prolongation.

Additional information is provided in the US package insert for quetiapine ([Northstar Rx LLC 2019](#)).

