1.3.1 Parkinson's Disease Psychosis Program

The scope of the development program for pimavanserin is the largest ever conducted in PDP. At the time of approval, 616 mostly older, late-stage PDP subjects had been evaluated in 16 countries over a span of >10 years. Clinically meaningful efficacy was established in Study ACP-103-020, a 6-week, placebo-controlled Phase 3 study ([Cummings et al. 2014](#)). This efficacy was supported by data from additional short-term Phase 2b/3 studies. In ACP-103-020, pimavanserin 34 mg consistently demonstrated statistically significant efficacy across multiple and independent endpoints, subject subgroups, and sensitivity analyses. Improvements in sleep and daytime wakefulness were also observed. These clinical benefits were achieved without worsening of PD motor symptoms and without a number of other safety concerns associated with atypical antipsychotics.

Pimavanserin is considered to be generally safe and well tolerated in patients with PDP. Across all clinical studies of pimavanserin, the most frequently reported treatment-emergent adverse events (TEAEs) were in the central nervous system (CNS), gastrointestinal, and psychiatric systems. Most events were mild to moderate in intensity. The most common CNS

TEAEs included dizziness (including postural), headache, and somnolence (drowsiness). Common gastrointestinal disturbances included dyspepsia, nausea, constipation, and vomiting. Severe nausea and vomiting were dose limiting in a few cases. Reported psychiatric conditions included agitation, insomnia, and confusional state.

Clinical and nonclinical safety pharmacology studies of pimavanserin suggest a potential risk for QT prolongation. The magnitude of effect in humans has been assessed in a thorough QT study with doses of pimavanserin ranging from 17 to 68 mg. In the Phase 3 PDP program, an average prolongation of approximately 5 to 8 ms was observed with pimavanserin 34 mg. In addition to a warning describing QT prolongation in the NUPLAZID® (pimavanserin) Prescribing Information ([ACADIA Pharmaceuticals Inc. 2019](#)), a boxed warning regarding the potential for increased risk of mortality in elderly patients with dementia-related psychosis taking atypical antipsychotics is present.

Additional information is provided in the pimavanserin IB and in the NUPLAZID® (pimavanserin) US package insert.

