4.2 Exclusion Criteria

A subject must meet none of the following exclusion criteria to be eligible for the study:

1. Has atypical parkinsonism (Parkinson's plus, multiple system atrophy [MSA], progressive supranuclear palsy [PSP]), or secondary parkinsonism variants such as tardive or medication-induced parkinsonism
2. Has undergone ablative procedures such as a pallidotomy, thalamotomy, or treatment with focused ultrasound
3. Is in hospice, is receiving end-of-life palliative care, or is bedridden or confined to a wheelchair (as defined by spending >80% of the day in a wheelchair)
4. Has neuropsychiatric symptoms that are primarily attributable to current delirium or substance abuse
5. Has current evidence of an unstable neurological, cardiovascular, respiratory, gastrointestinal, renal, hepatic, hematologic, or other medical or psychiatric disorder, including cancer or malignancies that, in the judgment of the Investigator, would jeopardize the safe participation of the subject in the study or significantly interfere with the conduct or interpretation of the study
6. Has a history of epilepsy
7. Has atrial fibrillation unless adequately anticoagulated
8. Has a history of myocardial infarction, unstable angina, acute coronary syndrome, or cerebrovascular accident within the last 6 months prior to Visit 1 (Screening)
9. Has any of the following:
 - a. greater than New York Heart Association (NYHA) Class 2 congestive heart failure
 - b. Grade 2 or greater angina pectoris (by Canadian Cardiovascular Society Angina Grading Scale)
 - c. sustained ventricular tachycardia
 - d. ventricular fibrillation
 - e. torsades de pointes
 - f. syncope due to an arrhythmia
 - g. an implantable cardiac defibrillator
10. Has a known history of a positive hepatitis B virus (HBV) or hepatitis C virus (HCV) test
11. Has a history of human immunodeficiency virus (HIV)

12. Has a history of neuroleptic malignant syndrome or serotonin syndrome
13. Has a known personal or family history of long QT syndrome or family history of sudden cardiac death
14. Has any of the following electrocardiogram (ECG) results at the Screening or Baseline visit:
 - a. If the subject is **not** on citalopram, escitalopram, or venlafaxine:
 - i. QTcF >450 ms, if QRS duration <120 ms
 - ii. QTcF >470 ms, if QRS duration \geq 120 ms
 - b. If the subject is on citalopram, escitalopram, or venlafaxine:
 - i. QTcF >425 ms, if QRS duration <120 ms
 - ii. QTcF >450 ms, if QRS duration \geq 120 ms

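### Section 4.6.1 and the Appendix A restricted-antimicrobial row name different decision-makers for QT-relevant antimicrobials after Baseline, and the row's only cardiac test is a pre-dose QTcF

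*Protocol*

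**What the plan says.** Protocol Section 4.6.1 sets the general rule: "Medications that can prolong QT interval are prohibited (or restricted if approved by the Medical Monitor) as specified in" Appendix A. It also says that "any questions regarding prohibited and restricted medications should be discussed with the Medical Monitor or designee". Appendix A refers back to Section 4.6.1 for procedures when a subject takes a prohibited or restricted drug.

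The Appendix A row for restricted antimicrobials, antifungals and antimalarials (azithromycin, ciprofloxacin, fluconazole, telithromycin and others) bars these drugs at Baseline. It then allows them during the study to treat a bacterial infection, "post-Baseline at the discretion of the Principal Investigator". The ECG condition for a narrow QRS reads "The subject has a Baseline ECG with a QTcF <425 ms IF QRS duration is <120 ms"; with QRS of 120 ms or more, the Baseline limit is below 450 ms. The row mentions neither the Medical Monitor nor any ECG taken after Baseline.

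Both active arms carry a QT signal. Section 1.3.1 reports that in the Phase 3 Parkinson's disease psychosis program "an average prolongation of approximately 5 to 8 ms was observed with pimavanserin 34 mg". Section 1.2.2 notes: "The quetiapine prescribing information also includes a warning regarding QT prolongation".

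**The concern.** The row makes these drugs conditional on QTcF, so it treats them as QT-relevant and they fall within the Section 4.6.1 rule. A site that reads the body text would seek approval from the Medical Monitor. A site that reads only the table would let the investigator decide.

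The ECG test also looks at the wrong time. When the permission can be used, two of the three arms are receiving a drug with a QT warning, and quetiapine is being raised from 25 mg to 50 mg and optionally to 100 mg. The investigator is blinded to the arm and to whether a dose increase was real, so the on-treatment tracing is the main subject-specific evidence of a QT effect. The row does not ask anyone to look at it before a further QT-relevant drug is added.

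What is at stake is subject safety in a population aged 50 to 85. Treatment comparisons are not involved.

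**Working it through.** The plan gives no figure to reproduce here. The check compares texts, then uses simple arithmetic to size the gap.

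**1. Who permits use.**
- Section 4.6.1: Medical Monitor approval for QT-prolonging drugs.
- Appendix A row: Principal Investigator discretion.
- If the reference to Appendix A meant that the row itself was the approval, the approval clause would do nothing, because the Appendix A table never mentions the Medical Monitor.
- If the two texts are combined, approval is required, but the row does not say so.

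Either way the wording needs reconciling.

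**2. When the ECG is tested.** SAP Section 5.3 defines Baseline as the last non-missing result before first dosing. The row's permission starts after Baseline, so its QTcF condition cannot reflect study drug.

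**3. Whether another rule fills the gap.**
- Table S-1 and Section 6.3.4 schedule a single ECG at each of Weeks 1 to 4, centrally read and clinician-reviewed, but do not tie the result to starting a restricted drug.
- The discontinuation rule in Section 6.3.4 concerns the Baseline tracing only.
- Section 4.4 lists no on-treatment QTcF stopping limit.
- The QTcF categories in SAP Section 14.4 are summaries for analysis.
- SAP Section 17 states that there is no monitoring committee.

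**4. What the Baseline limits absorb.** Criterion 14a, for subjects not on citalopram, escitalopram or venlafaxine, excludes "QTcF >450 ms, if QRS duration <120 ms" and above 470 ms for wider QRS. Distance from the row limit to those values:
- QRS <120 ms: 450 − 425 = 25 ms. After the mean pimavanserin effect: 25 − 8 = 17 to 25 − 5 = 20 ms.
- QRS ≥120 ms: 470 − 450 = 20 ms. After the mean effect: 20 − 8 = 12 to 20 − 5 = 15 ms.

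**5. The rise needed to pass an on-treatment limit.** Assume 450/470 ms as the limit; the documents set none on treatment. In whole milliseconds, the required rise is (limit + 1) − Baseline.

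| QRS | Baseline QTcF (ms) | Rise to exceed limit (ms) |
|---|---|---|
| <120 ms | 424 | 451 − 424 = 27 |
| <120 ms | 410 | 451 − 410 = 41 |
| <120 ms | 400 | 451 − 400 = 51 |
| ≥120 ms | 449 | 471 − 449 = 22 |
| ≥120 ms | 440 | 471 − 440 = 31 |
| ≥120 ms | 430 | 471 − 430 = 41 |

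From the highest allowed Baselines, these are 27/8 = 3.4 to 27/5 = 5.4 times the mean pimavanserin effect, or 22/8 = 2.8 to 22/5 = 4.4 times. The exposure is therefore to unusually large individual rises.

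**6. Subjects on citalopram, escitalopram or venlafaxine.** Criterion 14b already excludes "QTcF >425 ms, if QRS duration <120 ms" and above 450 ms for wider QRS. In whole milliseconds, the row removes only a subject at exactly 425 or 450 ms. It adds almost nothing for this group, because the stricter limit was applied at entry.

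**The case against.** The strongest reply is that Section 4.6.1 already requires Medical Monitor approval, that Appendix A sends the reader back to it, and that the investigator simply makes the clinical decision within that rule. This stands in part. A reader might infer from the row that nothing in the protocol makes approval a condition. Section 4.6.1 does not support that: the approval half is a conflict between two texts, not an absent safeguard. The same section also routes questions, and drugs that could interfere with study conduct, to the Medical Monitor.

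A reader might also infer that a Baseline QTcF is the row's sole condition. It is not: a bacterial infection is required, the limit depends on QRS, and several antimicrobials (moxifloxacin and clarithromycin among them) are prohibited outright in the same table.

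A third tempting reading is that subjects under criterion 14b have no safety margin, because the row and entry limits are the same numbers. That compares one pre-dose limit with another. Such a subject at the row limit has the same 25 or 20 ms to 450/470 ms as anyone else. Those remaining on these antidepressants must have had an unchanged dose for at least 4 weeks before Baseline, so the Baseline QTcF should already include that drug's effect.

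It is also fair that weekly ECGs make it unlikely that a prolonged tracing goes unseen, that Section 6.5 allows unscheduled safety evaluations, and that Appendix B advises caution with moderate CYP3A4 inhibitors, among which it lists ciprofloxacin and fluconazole. These reduce the risk, but none makes an on-treatment QTcF a condition of use. Finally, the latest tracing may be about a week old, and the Week 1 ECG largely reflects 25 mg quetiapine. The proposed check therefore answers the titration concern only partly, though it is still closer to the exposure than a pre-dose tracing.

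**Conclusion.** The point holds in two parts. First, Section 4.6.1 and the antimicrobial row disagree on who permits these drugs after Baseline. Second, the row's only cardiac condition predates study drug, and no rule elsewhere ties an on-treatment QTcF to starting the antimicrobial.

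The size is modest. The Baseline limits cover the 5 to 8 ms mean pimavanserin effect with 12 to 20 ms left. Passing the example limit needs a rise of at least 22 or 27 ms, depending on QRS. The documents do not say how often such rises occur and give no QT figure for quetiapine or the antimicrobials, so the risk cannot be quantified. The 450/470 ms values are entry limits borrowed as an illustration.

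No endpoint, estimate or error rate is affected. With enrollment permanently stopped after 11 subjects were randomized (SAP Sections 3.6 and 19), this is a low-priority, cheap improvement, useful mainly if the medication table is reused in a later study.

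**What to change.** Change the Appendix A restricted-antimicrobial row in two respects:

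- State that the Medical Monitor approval in Section 4.6.1 applies to this row, with prompt notification in place of prior approval when treatment is too urgent to wait. Carry the same urgent-treatment exception into Section 4.6.1, so that both places give one rule.
- Add that the most recent available on-treatment QTcF must be reviewed and be within a sponsor-set limit before the drug is started. The protocol's own 450 ms, or 470 ms with QRS of 120 ms or more, could serve as an example for the sponsor to confirm. If no on-treatment tracing exists yet, the Medical Monitor decides on the Baseline tracing; an unscheduled ECG remains optional under Section 6.5.

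The cost is protocol wording, since the Week 1 to 4 ECGs are already scheduled and centrally read. The downside is an occasional call to the Medical Monitor and a possible short delay or change of antimicrobial; the notification route limits the delay when treatment is urgent.
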